**Figure 12-1 Representation of Approach to Test Hypotheses**

Vertices with associated weights denote the individual null hypotheses and their local significance levels (initially the alpha is split 50%:50% across the primary null hypotheses regarding the two dose levels. Directed edges between the vertices specify how the local significance levels are propagated in case of significant results.

### **Statistical model for primary variable**

The primary efficacy endpoint is mean change in nasal polyp score from baseline to Week 16.

Baseline NPS is defined as the last measurement performed before the first dose of study drug. The absolute change from baseline NPS values will be defined as the NPS at the timepoint minus the NPS at baseline.

The primary efficacy variable will be analyzed using a mixed model repeated measures (MMRM) approach (fevipirant 450 mg plus SoC and fevipirant 150 mg plus SoC). The model will include change from baseline to follow-up timepoints every 4 weeks through week 16 as response variables, fixed-effects factors for treatment, visit, treatment  $\times$  visit interaction, nasal polyp score baseline value, and baseline  $\times$  visit interaction. An unstructured correlation structure will be assumed for the repeated measures within patients. Parameters will be estimated using the restricted maximum likelihood method with the Newton- Raphson algorithm. The least square mean change in nasal polyp score from baseline to week 16 alongside with 95% confidence interval and the P-value corresponding to the least square mean difference will be presented. The change in the least square mean will also be plotted against the visits to look at the general trend of the values across the visits.

The absolute change from baseline in NPS will be summarized by treatment arm and timepoint

### **12.4.3 Handling of missing values/censoring/discontinuations**

[figure not shown]
Despite all attempts to ensure complete follow-up for all patients, some patients may not be followed for nasal polyp size for the whole planned study duration of 16 weeks. The primary analysis will be done using a Mixed Model Repeated Measures (MMRM) approach. Under the assumption that the missing values are missing at random (MAR), this provides asymptotically unbiased and consistent estimates of the treatment effects.

### **12.4.4 Sensitivity and Supportive analyses**

**Sensitivity Analysis 1:** A responder analysis of patients achieving a reduction of at least 1 in the Nasal Polyp score would be performed using a logistic regression, including terms for treatment, visits and interaction between treatment and visit.

**Sensitivity Analysis 2:** The primary efficacy endpoint will be evaluated using the MMRM approach after imputing the Nasal Polyp Scores following surgery, only for patients who are considered as study withdrawals due to undergoing surgical procedures, by using the last observation carried forward (LOCF) technique. All other missing values will be imputed under the MAR approach within the MMRM model.

**Sensitivity Analysis 3:** The primary efficacy endpoint will be evaluated using the MMRM approach after imputing the Nasal Polyp Scores following surgery only for patients who are considered as study withdrawals due to undergoing surgical procedures, by using the worst

observed score for that patient. All other missing values will be imputed under the MAR approach within the MMRM model.

## 12.5 Analysis of secondary endpoints

The secondary objectives include:

**To evaluate the effect of symptoms as measured by the nasal congestion score with fevipiprant (150 mg or 450 mg once daily, separately) as compared to placebo, in terms of reduction in NCS from baseline to week 16.**

Nasal congestion is defined as the objective restriction of the nasal cavity airflow caused by mucosal pathology and or by mucosal secretions when anatomical variations have been excluded. The nasal congestion score is calculated based on the responses from the patients in Question 1 from the nasal congestion questionnaire outlined in [Section 16.4](#). The questionnaire has four questions relating to the symptoms of nasal obstruction with each question having four categories ranging from 0-3, where the scores relate to the degree of severity as follows:

- 0 = Not at all
- 1 = Mild
- 2 = Moderate
- 3 = Severe

The score however is calculated based on the response to the first question in the questionnaire.

The change in Nasal Congestion Score (NCS) will be analyzed using an MMRM model with visit, treatment, interaction between visit and treatment and the baseline average NCS as covariates. The least square mean change in Nasal Congestion Score from baseline to week 16 alongside with 95% confidence interval and the P-value corresponding to the least square mean difference will be presented.

**To evaluate the effect on quality of life as measured by the sino-nasal outcome test (SNOT-22) with fevipiprant (150 mg or 450 mg once daily, separately) , compared to placebo, in terms of increase in QoL score from baseline to Week 16.**

SNOT-22 measures the quality of life in patients facing nasal obstructions ([Section 16.5](#)). There are 22 items available on the questionnaire. Each item in the questionnaire are followed by five options to choose from:

- 0 = No problem
- 1 = Very Mild Problem
- 2 = Mild or slight Problem
- 3= Moderate problem
- 4 = Severe Problem
- 5 = Problem as bad as it can be.

The scores for each of the items are added to get a total out of 110, with 110 being the worst signifier of quality of life. Also the questionnaire has the option for the patient to select the five most important items affecting their health which are analyzed separately to give a rating across the patients. The treatment group difference in terms of change from baseline at Week 16 in

SNOT-22 will be estimated using an MMRM model with change from baseline as the response variable, adjusted for visits (Week 4, 8, 12 and 16), treatment, interaction between visit and treatment and baseline SNOT-22.

The least square mean change in SNOT-22 Score from baseline to week 16 alongside with 95% confidence interval and the P-value corresponding to the least square mean difference will be presented.

**To evaluate the effect on smell as measured by the university of Pennsylvania smell identification test (UPSIT) with fevipiprant (150 mg or 450 mg, once daily) ,compared to placebo, in terms of increase in smell score from baseline to Week 16.**

The university of Pennsylvania smell identification test (UPSIT) is a test for smell identification to test an individuals olfactory response. The test is a measure of an individual's ability to detect odor. It consists of 4 workbooks of 10 questions, giving a total of 40 questions. On each page, there is a different "scratch and sniff" strip which are embedded with a microencapsulated odorant. There is also a four choice multiple choice question on each page. The scents are released using a pencil. After each scent is released, the patient smells the level and detects the odor from the four choices. There is an answer column on the back of the test booklet, and the test is scored out of 40 items. The score is compared to scores in a normative database from 4000 normal individuals, this tells the level of absolute smell function. The score also indicates how the patient does in accordance to their age group and gender. The maximum score achievable on the scale is 40.

The treatment group difference in terms of change from baseline at Week 16 in UPSIT will be estimated using an MMRM model with change from baseline as the response variable, adjusted for visits (week 4, 8, 12 and 16), treatment, interaction between visit and treatment and baseline UPSIT. The least square mean change in UPSIT Score from baseline to week 16 alongside with 95% confidence interval and the P-value corresponding to the least square mean difference will be presented.

**To evaluate the general safety and tolerability of fevipiprant (150 mg and 450 mg, separately) as compared to placebo.**

Safety and tolerability assessments were based on the incidence of adverse events and serious adverse events, as well as vital signs, clinical laboratory evaluation, and 12-lead electrocardiogram findings.

### **12.5.1 Safety Variables**

For all safety analyses, the safety set will be used. All listings and tables will be presented by treatment group. Safety summaries will be primarily based on on-treatment data with selected tables also presented for the all data after the first intake of study drug, while all databased safety data will be listed. The on-treatment period lasts from the date of first administration of study treatment to 30 days after the date of the last actual administration of any study treatment.

#### **Adverse events**

Adverse events starting on or after the time of first intake of study drug and until the 30 days after the last intake of study drug will be classified as treatment-emergent adverse events. Any adverse events that started during the study after informed consent before the time of first intake

of the study drug will be classified as a prior adverse event and not included in tabulations of treatment emergent adverse events.

The following treatment emergent adverse event summaries will be produced,

- overall by system organ class and preferred term,
- overall by system organ class and preferred,
- overall by system organ class, preferred term and maximum severity,
- suspected drug related adverse events by system organ class and preferred term, and
- adverse events leading to permanent discontinuation of study drug by system organ class and preferred term.

Serious adverse events, non-serious adverse events, adverse events requiring dose adjustment or study-drug interruption adverse events requiring additional therapy during the on-treatment period will be summarized.

The adverse events of special interest (AESI) will be listed and summarized by treatment group.

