### 10.1.2 Serious adverse events

An SAE is defined as any adverse event [appearance of (or worsening of any pre-existing)] undesirable sign(s), symptom(s) or medical condition(s) which meets any one of the following criteria:

- fatal
- life-threatening

Life-threatening in the context of a SAE refers to a reaction in which the subject was at risk of death at the time of the reaction; it does not refer to a reaction that hypothetically might have caused death if it were more severe (please refer to the ICH-E2D Guidelines).

- results in persistent or significant disability/incapacity
- constitutes a congenital anomaly/birth defect
- requires inpatient hospitalization or prolongation of existing hospitalization, unless hospitalization is for:
  1. routine treatment or monitoring of the studied indication, not associated with any deterioration in condition under study
  2. elective or pre-planned treatment for a pre-existing condition that is unrelated to the indication under study and has not worsened since signing the informed consent
  3. social reasons and respite care in the absence of any deterioration in the subject's general condition
  4. treatment on an emergency outpatient basis for an event not fulfilling any of the definitions of a SAE given above and not resulting in hospital admission
- is medically significant, e.g. defined as an event that jeopardizes the subject or may require medical or surgical intervention to prevent one of the outcomes listed above

Medical and scientific judgment should be exercised in deciding whether other situations should be considered serious reactions, such as important medical events that might not be immediately life-threatening or result in death or hospitalization but might jeopardize the subject or might require intervention to prevent one of the other outcomes listed above. Such events should be considered as "medically significant". Examples of such events are intensive treatment in an emergency room or at home for allergic bronchospasm, blood dyscrasias or convulsions that do not result in hospitalization or development of dependency or abuse (please refer to the ICH-E2D Guidelines).

All malignant neoplasms will be assessed as serious under "medically significant" if other seriousness criteria are not met.

Any suspected transmission via a medicinal product of an infectious agent is also considered a serious adverse reaction.

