### **Clinical laboratory evaluations**

All laboratory data will be listed with abnormal values flagged.

All laboratory parameter values will be classified into one of the four mutually exclusive groups (low, normal, high, and low + high).

For selected laboratory parameters, the number and percentage of patients with newly occurring or worsening on-treatment laboratory abnormalities meeting the clinically notable will be summarized by laboratory parameter at any time-point over the treatment period, considering all post-baseline data from scheduled, unscheduled and premature discontinuation visits. Patients with any newly occurring or worsening on-treatment value meeting the clinically notable criteria will be counted under the applicable criteria.

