2.1.3.9 On-treatment assessment/event and observation periods

The overall observation period will be divided into three mutually exclusive segments:

1. **pre-treatment period**: from day of patient's informed consent to the day before first administration of study treatment
2. **on-treatment period**: from date of first administration of study treatment to date of last actual administration of any study treatment +1 day (including start and stop date)
3. **post-treatment period**: starting at day 1 after last administration of study treatment.

Safety summaries (tables, figures) include data from the pre-treatment period (to display the baseline status e.g. for ECG) and the on-treatment period. Data from the post-treatment period with the exception of deaths should not be included unless requested from Health Authorities or external committees.

In particular, summary tables for adverse events (AEs) will summarize only on-treatment events, with a start date during the on-treatment period, the so-called **treatment-emergent** AEs.

However, all safety data (including those from the post-treatment period) will be listed and those collected during the pre-treatment and post-treatment period are to be flagged.

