2.7.5 Adverse events (AEs)

Adverse events after informed consent including asthma exacerbations will be listed.

Adverse events starting on or after the day of the first intake of study drug and until the day after the last intake of study drug will be classified as treatment emergent adverse events. Adverse events that started during the study after informed consent and before the day of the first intake of study drug will be classified as prior adverse events and not included in tabulations of treatment emergent adverse events.

The number and percentage of patients who reported TEAEs will be summarized by primary system organ class (SOC), preferred term (PT), and treatment group for

- all adverse events (AEs)
- all AEs by maximum severity
- AEs suspected to be related to study drug
- AEs by standardized MedDRA query (SMQ) level serious AEs (SAEs)
- AEs leading to permanent study drug discontinuation
- Serious adverse events

Unless otherwise specified, primary system organ classes will be sorted alphabetically and, within each primary system organ class, the preferred terms will be sorted in descending order of frequency in the QAW039 150 mg once daily and QAW039 450 mg once daily treatment group. If a patient reported more than one AE with the same preferred term, the AE will be counted only once. If a patient reported more than one AE within the same primary system organ class, the patient will be counted only once at the system organ class level. In addition, the most frequent AEs will be presented by preferred term in descending order of frequency in the QAW039 150 mg QAW039 450 mg once daily treatment group.

Serious adverse events will also be summarized.

In addition, the most frequent AEs will be presented by preferred term in descending order of frequency in the QAW039 150 mg once daily treatment group.

All adverse events and related preferred terms and system organ class will be categorised using latest MedDRA version available at the time of data analysis.

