2.7.5.1 Adverse events of special interest / grouping of AEs

The number and percentage of patients and treatment emergent adverse events of special interest will be summarized for each type of event with a break-down for each type of event by

SMQ(when applicable) and preferred term. The Compound Case Retrieval Strategy (CRS) will be used to determine the MedDRA search criteria to be used to identify events of special interest.

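### Treatment emergence is decided by start date alone, so a screening or run-in adverse event that worsens on study drug is left out of the SAP's TEAE tables

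*Protocol*

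**What the plan says.** Protocol 12.5.1 (Adverse events) counts as treatment-emergent "Adverse events starting on or after the time of first intake of study drug", up to 30 days after the last intake. An event that began between consent and first intake "will be classified as a prior adverse event and not included in tabulations of treatment emergent adverse events".

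The SAP keeps the same front end. Under 2.7.5, events that begin after consent and "before the day of the first intake of study drug will be classified as prior adverse events". Section 2.1.3.9 applies this to AE summary tables generally, which "will summarize only on-treatment events, with a start date during the on-treatment period". Section 2.7.5 introduces its table list with "The number and percentage of patients who reported TEAEs will be summarized". That list covers all AEs, maximum severity, suspected relationship, serious AEs and AEs leading to permanent discontinuation. In 2.7.5.1, "treatment emergent adverse events of special interest will be summarized", and the registry-disclosure tables in 2.7.5.2 are also treatment-emergent.

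Pre-treatment events are still listed and flagged (SAP 2.1.3.9). Neither document has a clause for an event that started before dosing and got worse afterwards.

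**The concern.** An event already present at first dose that deteriorates on drug is a possible safety signal. A rule that looks only at onset removes it from the comparison between arms. AEs are collected from consent, through screening and a four-week run-in in which all patients start mometasone and leukotriene receptor antagonists are stopped (Protocol 6.1.2), so events with onset before dosing are to be expected.

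Safety and tolerability is a secondary objective, assessed with about 31 patients per arm. At that size, one or two events can change how a table reads. Two tables could also disagree. The disposition summary (SAP 2.3.1) reports the primary reason for stopping treatment with no condition on AE onset. It could show a discontinuation for an adverse event that the AE-discontinuation table does not contain.

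**Working it through.** The plan states no figure to reproduce. The check is to follow one event through the tables: a mild AE with onset in run-in that becomes severe and serious after first dose and is the reason for stopping study drug.

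1. **Classification.** Its start date precedes first intake, so it is a prior AE under Protocol 12.5.1 and SAP 2.7.5. Nothing in either section reclassifies it.
2. **TEAE tables in SAP 2.7.5** (overall, maximum severity, related, serious, permanent discontinuation): not counted, because all are TEAE tables and 2.1.3.9 requires an on-treatment start date.
3. **Special interest (2.7.5.1) and disclosure (2.7.5.2):** not counted, because both are restricted to treatment-emergent events.
4. **Deaths (2.7.6):** selected by date of death, not AE onset. If the event were fatal on treatment it would be tabulated by system organ class and preferred term.
5. **Listings:** present, flagged as pre-treatment.
6. **Disposition (2.3.1):** can appear as an AE discontinuation.

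Next, could data entry bring the event back with a new start date?

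- Protocol 10.1.1 asks for the severity grade and the start and end dates of an event. It gives no instruction to open a second record when the grade changes.
- Protocol 10.1.3 has progression of an SAE sent in as follow-up to the original episode, which keeps the pre-dose onset. A new report is required only for an SAE in a different time interval or one considered completely unrelated.
- SAP 2.7.5.2 merges consecutive same-term records separated by at most one day. It therefore allows for split records, but only for disclosure counts, and it does not require splitting.

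Size of the exposed window:

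- Pre-dose collection: run-in of 4 weeks plus screening of up to 2 weeks (Table 8-1; Protocol 8.1), so 4 to 6 weeks.
- On drug: 16 weeks.
- Pre-dose share of onset time at a constant rate: 4/(4+16) = 20% to 6/(6+16) = 27%.

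This is a share of onset time, not of events that worsen. To be affected, an event must also still be present at first dose and then deteriorate, and the documents give no rate for either. Protocol 5.2 makes a constant rate doubtful among randomized patients: an asthma exacerbation before randomization means screen failure, and acute sinusitis, nasal infection or upper respiratory infection in run-in is exclusionary.

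The documents also differ on the end of the window (30 days after last intake in the protocol, 1 day in the SAP). That needs reconciling but does not affect this point, which concerns the start of the window.

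**The case against.** The strongest reply has four parts.

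**Not every table is affected.** A reader might infer that such an event vanishes from all AE summaries. The documents do not support that. The deaths summary would include a fatal one. The protocol's sentence on serious, non-serious and dose-adjustment AEs in the on-treatment period does not repeat the start-date condition, and the protocol promises some unspecified tables for all data after first intake. On the protocol alone, the reach of the rule is arguable. For the SAP's TEAE tables, 2.1.3.9 and 2.7.5 settle it against inclusion.

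**Recording may already cover part of it.** Conditions present at consent go to medical history (10.1.1), and the SAE definition speaks of "appearance of (or worsening of any pre-existing" conditions. A serious worsening of asthma or another comorbidity can therefore be an event in its own right with a post-dose start. Table 8-3 also has significant post-dose examination findings that meet the AE definition recorded as AEs. This stands, and it narrows the gap to AEs with onset between consent and first dose. Sites might also split records under eCRF instructions that are not part of these documents, so actual loss cannot be shown.

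**The laboratory contrast does not help.** A reader might argue that the plan already counts worsening elsewhere, since the protocol tabulates "newly occurring or worsening on-treatment laboratory abnormalities". SAP 2.7.7.2, however, counts a worsening notable value only when baseline was not notable, and 2.8.2 takes the same approach for vital signs. Those tables do not count deterioration from an already notable baseline, so they are no precedent.

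**The events are listed.** True: they leave the comparison between arms, not the record.

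**Conclusion.** The point holds in limited form. As written, the start-date rule keeps on-drug worsening of a screening or run-in AE out of the SAP's TEAE-based tables for overall incidence, severity, relationship, seriousness, discontinuation, special interest and disclosure, apart from deaths. This is a stated rule that gives an incomplete safety comparison, not merely an unwritten detail.

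A count of lost events cannot be given, because the documents contain no AE or worsening rate. The only supportable figure is the 20–27% share of onset time, which rests on a constant rate and says nothing about how many events worsen. The conclusion assumes that sites keep one record per event, which is what the text implies but does not state. The efficacy analyses are untouched. It should be corrected, but it does not put the trial's main conclusion at risk.

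**What to change.** - **Definition.** In Protocol 12.5.1 and SAP 2.1.3.9 and 2.7.5, define a treatment-emergent AE as one that starts on or after first intake, or one that started earlier and increased in severity or became serious on or after first intake. Date it at the worsening.
- **Recording.** In the eCRF completion instructions, have sites enter the worsening as a new AE record with its own start date. Word this to be consistent with Protocol 10.1.3, for example by keeping the safety report as follow-up to the original episode while the AE page carries the new dated record.
- **Discontinuation table.** Select it by the date study drug was stopped, so that a prior AE that ends treatment without a change of grade is also counted and the table agrees with disposition.

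The cost is a short change to the protocol, made by written amendment (Protocol 14.1), and to the SAP, plus an eCRF note. TEAE counts would rise slightly in all arms, and AEs already recorded with pre-dose onset would need some querying for dates of worsening.
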